- [name], Chief Paediatric Radiologist

Central Hospital of Päijät-Häme, Department of Surgery

[name]

- [name], PhD, Orthopaedic Surgeon

Clinical Investigation Plan

Bioabsorbable Intramedullary Nail Fixation of Forearm Fractures in Children

Synopsis

Name of Sponsor: Bioretec Ltd.
Name of Medical Device: Bioabsorbable Intramedullary Nail
Title of Study: Bioabsorbable Intramedullary Nail Fixation of Forearm Fractures in Children
Investigators: 
○ [name], PhD, Associate Professor, Paediatric Surgeon○ [name], PhD, Orthopaedic Surgeon○ [name], Statistician○ [name], MB, PhD candidate○ [name], Paediatric Radiologist○ [name], Professor, MD, PhD, Paediatric Orthopedist and Surgeon○ [name], [name], PhD, Paediatric Orthopedist and Surgeon
Study Centres: 
- Oulu University Hospital, Department of Children and Adolescents- Central Hospital of Päijät-Häme, Department of Surgery, Unit of Paediatric Surgery
Studied Period (weeks): 52 (follow up 2 years) Date of First Enrolment: 2010 Date of Last Completed: 2018
Objectives: 
Primary objective: Clinical outcome of the fracture treatment is equal between patients treated by the new bioabsorbable medical device and by standard of care using a titanium alloy device. This will be assessed by functional and clinical outcome measuring range of motion of forearm, wrist and elbow and pain assessment at two-years' follow-up.
 
Secondary objective: The new medical device (bioabsorbable intramedullary nail) is at least as good as the routinely used device (elastic stable titanium alloy intramedullary nail) in forearm fracture treatment to achieve a level of reduction and stabilisation that is appropriate to the age of the child. This will be assessed by radiological outcome and determination of bony union formation and alignment in the healing forearm fracture using radiographic methods; further, soft-tissue and bone-tissue reactions are to be evaluated by MRI.

Methodology:

Clinical Investigation Plan

Bioabsorbable Intramedullary Nail Fixation of Forearm Fractures in Children

The fracture is fixed using the new medical device (bioabsorbable intramedullary nail) or the standard titanium intramedullary nail.

Number of Patients: At most 2 pilot operations / study centre + Planned 13 operations required for analysis; Total 35 patients to be enrolled, appreciating the potential drop-outs.

Diagnosis and Main Criteria for Inclusion and Exclusion:

Diagnosis:

Children with an unstable midshaft (diaphyseal) forearm (radius and/or ulna) fracture.

Main inclusion and exclusion criteria: The subject and/or guardian has signed and dated the informed consent, the subject is 5 to 16 years of age, the subject has no previous fracture or infection of the study region, no metabolic bone disease, no systematic disease or medication affecting bone quality or resistance to infection.

Medical Test Device installation and identification:

The device is surgically implanted. The batch of device is identified by test device name, packaging date and clinical investigation number A2228-CIP-1.

Duration of Treatment:

The follow-up of the patients will be 104 weeks (2 years). The control device will be removed 6 months after operation. The bioabsorbable device is expected to retain its mechanical functionality for at least 8 weeks, while the complete bioabsorption of the device in human body is expected to take place within approx. 2 years.

Criteria for Evaluation:

Repeated examination of functional, clinical and radiographic outcome, and bone union formation by range of motion measurement, radiography (plain radiographs). Magnetic resonance imaging for a randomly selected subgroup of at least 10 patients treated by test device, general questionnaires.

Efficacy:

The success of fixation will be determined by radiographic measurements in comparison between the immediate postoperative state and 6, 12 and 26 weeks after surgery.

Safety:

Continuous evaluations of safety parameters and specific evaluations of adverse events and serious adverse events will take place at each postoperative study visit. The safety variables to be evaluated include adverse events, findings from physical and radiographic examinations, subjective reports of pain and functional outcome assessments.

Statistical Methods:

The primary variable will be analysed using an analysis of variance model for repeated measurements. Treatment differences with 95% confidence intervals will be calculated from the model.

Identification of the Investigational Device

Investigational devices for intramedullary nail fixation are manufactured by Bioretec Ltd. Devices are intended for forearm fracture repair of radial and/or ulnar shaft. The main purpose of the device is to achieve a level of reduction and stabilisation of fracture that is appropriate to facilitate the uneventful bone healing, thus restoration of the pre-trauma anatomical structure, taking into account the age of the child. In addition, the need for the second operation to remove hardware will be obviated by the investigational devices.

Devices are made of bioabsorbable oriented high-strength poly(lactide-co-glycolide) (PLGA) 85:15. The diameter of the IM nails is 2.0 mm, 2.7 mm or 3.2 mm. The nails are 400 mm long and in the tips of the nails there are x-ray positive markers. The high strength of IM nails is result of special orientation techniques applied in the manufacturing of the products at Bioretec Ltd. The corresponding shorter product, ActivaPin™ is registered product, which has been on the EU and US markets already several years.

Prior training in the insertion techniques of bioabsorbable devices is recommended.

Identification of the Control Device

Commonly used titanium elastic nail (TEN) manufactured by SynthesDePue Inc. is used as a control device in this study. According to routine clinical practices, the control device LOT number is documented into CRF. The main purpose of the device is to achieve a level of reduction and stabilisation of fracture that is appropriate to facilitate the uneventful bone healing, thus restoration of the pre-trauma anatomical structure, taking into account the age of the child. Prior training in the insertion techniques of TEN nails is recommended.

Preliminary Investigations and Justification of the Study

The purpose of this prospective, randomized clinical trial is to assess the efficacy and safety of a bioabsorbable device in fixation of forearm fracture patients. As the primary endpoint, the bioabsorbable intramedullary nail is expected to act as efficiently as the routinely used TEN nails in stabilization of forearm fractures in pediatric patients with unstable radius and/or ulna fractures.

Literature Review

Closed reduction and plaster cast immobilization provides in most cases of children's forearm fractures sufficient stability for an uneventful healing of the fracture and gives a satisfactory end result. [1-5] The satisfactory results are achieved due to rapid healing and remodelling of angulations in children.

However, in cases of

- unstable fractures (e.g. midshaft diaphyseal forearm fractures),
- fractures with unacceptable alignment and fracture dislocations,
- open fractures,
- segmental fractures,
- proximal fractures that will not remodel as predictably and
- those with associated neurovascular compromise

an operative treatment is often mandatory to avoid residual deformity with permanent loss of forearm rotation. [1, 3, 6-9] Remodeling will not correct rotational deformities of the distal third of the forearm; for that reason, rotational deformities must be often treated operatively. [2] In addition, in an older child ability for fracture remodeling and correction of deformity is not as effective as in a younger child, therefore the operative treatment of displaced forearm fractures is often recommended in children older than 10 years of age and in younger children when conservative treatment fails.

Effective operative alternatives of unstable fractures include open reduction and internal fixation (ORIF) with plates and screws or mini-open reduction and intramedullary (IM) nailing. [1, 8-10] The choice of fixation usually is a matter of surgeon preference.

Plate fixation allows anatomic reduction and early motion with most studies showing good outcomes in the pediatric population. However, plate fixation requires a large surgical approach and smaller children may have bones that are too narrow to accommodate a plate. [8] In addition, incision for a plate fixation is greater than that required for IM nailing. In contrary to TEN nailing if plate fixation is applied the injured area of bone is exposed. This may also have a negative effect on the healing of the fracture by disturbing the haematoma and callus formation and increase complication possibilities, like infection. Plate removal is also associated with significant complications, such as nerve injury, and in addition, the removal of plate may be difficult due to scarring and bone growth over the plates. [9]

Flexible intramedullary nailing of pediatric forearm fractures has shown also excellent results. [2, 7, 9-12] The advantages of closed reduction and IM nailing include a minimally invasive

Clinical Investigation Plan

Bioabsorbable Intramedullary Nail Fixation of Forearm Fractures in Children

form of treatment of pediatric fractures and avoiding large incisions, shorter procedures, and ease of hardware removal, with a lower refracture rate compared with plates. [2, 10] Usually, TEN nails can be placed without disturbing the fracture site in some cases; however, in others the fracture is open, reduced, and fixated with the nail. Titanium elastic nails are a popular choice, but rush rods and Steinman pins/Kirschner wires also are used. [7, 10-13]

The inherent disadvantageous of these metallic devices are stress shielding phenomenon, pain and local irritation. [14, 15] Retained metallic implants provide an attractive and stable host surface for intraoperatively derived bacteria and possess the risk of endogenous infection. Release of metallic ions from these implants has been documented, though the long-term effects of these are not yet known. Because of these reasons in the use of metallic IM nails there is also need for a second operation to remove hardware after the bone has healed. The removing of IM nail is performed when the full healing has occurred, usually 4 - 6 months after operation, but the nails are removed earlier if a bridging callous is present and the hardware is prominent or painful. Generally, the removal operation of metallic devices has significant economic implications, including the costs of the procedure as well as possible work time lost by the parents accompanying the removal operation. Especially for the pediatric patients and their parents the removal operation causes needless discomfort and concern. The removal operation also always possesses the risk of anesthesia complications and infection. The problems presented above have led to the development of bioabsorbable IM nails.

Bioabsorbable devices and IM nails

During the last decades bioabsorbable implants made utilizing orientation techniques have gained a wide acceptance in the treatment of various cancellous bone fractures and osteotomies. Due to their complete biodegradation character the need for a second operation for removal of the device is overcome and long-term interference with children's growing skeleton is avoided. These implants also offer the advantages of gradual load transfer to the healing tissue, reduced risk of peri-implant osteoporosis and infection. An important aspect is that these implants do not interfere with clinical imaging after surgical implantation. [15]

In paediatric orthopaedics Bostman et al. showed that self-reinforced absorbable rods were suitable for fixation of physeal fractures in children. [16] In 1991, Hope et al. had compared the self-reinforced absorbable rods with metallic fixation of elbow fractures in children. [17] Partio et al found SR-PLLA screws firm enough for fixation of subtalar extra-articular arthrodesis in children. [18] Bioabsorbable fixation technique for pediatric olecranon fractures has been described, with the advantage of avoiding reoperation to remove hardware. [19]

Clinical Investigation Plan

Bioabsorbable Intramedullary Nail Fixation of Forearm Fractures in Children

Favorable results on treatment of forearm fractures by bioabsorbable intramedullary nails was gained already in the 1990. [20-22] In that study the poly-L-lactide (PLLA) IM-rods seemed to be a viable option in the treatment of children's fore-arm fractures, based on 3,5 years follow-up carried out in this study.

Bioretec's ActivaPin™ products have gained excellent clinical outcome in the different indications of orthopedics and trauma surgery. The modified (lengthened) bioabsorbable devices for fixation of children's unstable forearm fractures are manufactured by Bioretec Ltd based on ActivaPin™ technology. Devices are intended for repair of children's unstable forearm (radius and/or ulna) fractures. In addition to extended length an X-ray marker has been added to the tip of the implant to facilitate the similar insertion technique applied for TEN nails, which utilizes fluoroscopy to monitor the position of the tip of the implant intra-operatively. The main purpose of the device is to stabilize diaphyseal forearm fractures of children in the alignment of the repositioned state for at least 6 weeks in the presence of appropriate immobilization and to obviate the need for second operation to remove the hardware. The operation technique of these bioabsorbable IM nails is very similar to that of metallic IM nails.

Preclinical Testing

Preclinical testing is not applied, as the materials have known toxicological profiles and well-established track record of safe clinical use in other application areas comparable to intramedullary nail fixation of forearm fractures. The manufacturing methods of bioabsorbable IM nails are well established in manufacturing of similar implants to different application areas.

Risk Analysis and Risk Assessment

The risk management of this clinical investigation has been made according to current risk management standard for medical devices (ISO 14971) and according to risk assessment the residual risk is acceptable. Based on risk assessment the risk is negligible that the 85/15 PLGA implants would cause any bioincompatibility reactions in this indication. The residual risk of each hazard was estimated based on the probability and severity of occurrence.

Objectives

Primary Objectives

The primary objective of the study is to evaluate the feasibility and efficacy of the new medical device in treatment of paediatric patients with forearm fractures. The key variables in this assessment are the evaluation of the functional and clinical outcome by measuring range of motion in forearm, wrist and elbow (e.g. measuring supination/pronation and flexion-extension movements), and subjective pain assessment during recovery. The primary objective will be met if these outcomes in the treatment group are at least comparable to those of the patients treated with standard of care (TEN nail), interpreted by using the Price's classification system (<15 degrees of change in motion range is excellent clinical outcomes), and Flynn's criteria for upper extremity assessment (<10 degrees of change in motion range justifies satisfactory outcomes). The potential difference less than 10 degrees are to be determined not clinically significant. The raw results of clinical measurements and statistical significance of each finding are to be reported.

Secondary Objectives

The secondary objectives of the study are to evaluate the radiographic outcome of the forearm fracture treatment in patients treated using the study device. The key variables in assessment of these objectives are:

- fracture reduction and angulation,
- formation of bridging callus and consolidation (union, delayed union, non-union and malunion)

The method in assessment of key variables is plain radiographic evaluation. The secondary objective will be met if these outcomes in the treatment group are at least comparable to those of the patients treated with standard of care (TEN nail). According to the previous literature, angular deformity of <10 degrees in radius and/or ulna is to be determined not clinically significant [27-29].

Soft-tissue reaction against the biodegradable implant are to be studied by Magnetic Resonance Imaging (MRI) for a randomly selected sub-group of at least 10 patients.

Design of the Clinical Investigation

Type and Design of The Study

This is a randomized parallel-group **two-centre** study on the use of bioabsorbable intramedullary nail device for fixation of the radial and ulnar shaft fractures in children. All patients will receive the standard of care for other injuries caused by the trauma.

35 subjects will be enrolled at the University Hospital of Oulu and Central Hospital of Päijät-Häme to appreciate the potential drop-outs. The minimum number of patients in both groups (study implant vs. titanium implant) is 13. To minimize any selection bias, the patients will be sequentially randomized into these groups.

The study cannot be executed in a blinded fashion, because the orthopaedic surgeon and the operating room staff will inevitably be aware of the type of the implanted device. The patient must be also informed if the signed implant needs removal: the titanium alloy devices will be removed at 6 months, while the absorbable device will not require removal surgery.

Selection of the Study Population and Enrollment

The study begins with the signing and dating of the informed consent. All subjects and/or guardian must provide informed consent. During the consent procedure, the person obtaining consent must inform the subject of all elements of informed consent. Adequate time must be allowed for the subject to ask questions and make a voluntary decision. No protocol-specific procedures, including screening procedures, are performed until the subject has signed and dated the independent ethics committee approved informed consent form. Subjects must also meet the inclusion and exclusion criteria to be enrolled in the study. The participation in this clinical investigation is voluntary and the subject may interrupt the participation at any time, which is to be clearly informed.

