1.1.7 Visit Schedule

For each subject, the study consists of assessments preoperatively, immediately after operation and the follow up visits postoperatively. The recommend time window of scheduled visits is ± 7 days. The clinical assessments and procedures performed at each visit are shown in Table 2.

Clinical Investigation Plan

Bioabsorbable Intramedullary Nail Fixation of Forearm Fractures in Children

During these visits will be investigated: function of both arms, radiological fracture healing, well-being and incidence of complications.

Table 2 Assessment and procedures at each visit

Assessment	Operation		4 week	12 weeks	26 weeks	52 weeks	104 weeks
	Pre-operative	Post-operative					
	Visit 1	Visit 2	Visit 3	Visit 4	Visit 5	Call 6	Visit 7
Informed consent, inclusion and exclusion criteria	X						
Demographics, medical history	X						
Injuries and comorbidities	X						
Randomization	X						
Fracture reduction and fixation	X						
Cast removal			X				
TEN nail removal					X		
Primary performance variable	Operation		4 week	12 weeks	26 weeks	52 weeks	104 weeks
	Pre-operative	Post-operative					
	Visit 1	Visit 2	Visit 3	Visit 4	Visit 5	Call 6	Visit 7
Functional and clinical outcome evaluated by measuring rate of motion			X	X	X		X
Pain assessment		X	X	X	X	X	X
Subjective		X	X	X	X	X	X

Clinical Investigation Plan

Bioabsorbable Intramedullary Nail Fixation of Forearm Fractures in Children

result							
Secondary variables	Operation		4 week	12 weeks	26 weeks	52 weeks	104 weeks
	Pre-operative	Post-operative					
	Visit 1	Visit 2	Visit 3	Visit 4	Visit 5	Call 6	Visit 7
Radiographic outcome and bone union formation evaluated by plain radiographs	X	X	X	X	X		X
Radiographic outcome and bone union formation evaluated by MRI imaging		X*		X*		X*	X*
Safety and tolerability variables	Operation		4 week	12 weeks	26 weeks	52 weeks	104 weeks
	Pre-operative	Post-operative					
	Visit 1	Visit 2	Visit 3	Visit 4	Visit 5	Call 6	Visit 7
Adverse events	X	X	X	X	X	X	X
Concomitant medications	X	X	X	X	X	X	X
Conclusion of participation							X

* Radiographic outcome and bone union formation of 5-10 subjects will be evaluated by MRI imaging immediately after operation and three follow up visits

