1.1.10 Radiographic Evaluations

This study will involve normal repeated radiographic examinations of the forearm for assessment of outcome, progress of fracture union and also possible development of complications related to injury or treatment.

Plain Radiographs

The plain radiographs in standard anteroposterior (AP) and lateral projections will be taken before and after surgery, followed by repeated radiographs according to table 2.

The parameters defined from forearm's plain radiographs are

- fracture reduction and retention
- fracture angulation
- fracture union as bridging callus by the presence of obliteration of fracture lines (union, delayed union, non-union)
- increased/decreased radial bow (fracture malunion)
- limb-length discrepancy
- complications related to injury or treatment (implant-related osteolysis)

Clinical Investigation Plan

Bioabsorbable Intramedullary Nail Fixation of Forearm Fractures in Children

The angulation of the fractures will be measured on anteroposterior and lateral radiographic views. Radiographic union will be defined as the presence of bridging callus at all visualized cortices on the anteroposterior and lateral radiographic views. Delayed union will be classified as incomplete healing at 10 weeks in children <9 years of age and at 12 weeks in children ≥9 years of age. [23]

At latest follow-up malunion will be quantified by measurement of the amount and location of the maximum radial bow in relation to the contralateral, normal forearm as described by Schemitsch and Richards. The radial bow will be measured on the anteroposterior radiograph of the forearm, which includes the wrist and elbow joints.

Limb-length discrepancy will be assessed by measurement of the distances between lateral epicondyle of the humerus and radial styloid process in both limbs.

MR Imaging

The parameters defined from forearm's MR images are

- fracture reduction and retention
- fracture angulation
- fracture union as bridging callus by the presence of obliteration of fracture lines (union, delayed union, non-union)
- fracture malunion (radial bow, Limb-length discrepancy)
- complications related to injury or treatment (implant related osteolysis and detection of IM nail failure)
- soft-tissue reactions (oedema, abnormal fibrotic tissue, post-traumatic calcification) in the surroundings
- bioabsorption of the investigational device

Evaluation of Variables

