1.1.12 Secondary Variables

Forearm's plain radiographs in AP and lateral projections and MRI imaging will be used to determine:

- Fracture reduction and retention
- Fracture angulation, expressed as degrees \pm SD (graded according to Table below)
- Bony union formation and rate (union, delayed union, non-union, malunion)

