1.1.13 Safety Variables

Incidence of adverse events (AE) and serious adverse event (SAE) will be expressed as proportion per group. These consist of e.g. complications related to injury or treatment and will be separated into resolved versus long-term or non-resolved complications, which included a need for return to the operating room. Monitored AE's are:

Clinical Investigation Plan

Bioabsorbable Intramedullary Nail Fixation of Forearm Fractures in Children

- Fracture delayed union, nonunion and malunion
- Incidence of infection
- Intra-operative complications related to fixation hardware
- Need for secondary reduction due to fracture instability
- Osteolysis
- Biocompatibility reactions
- Mechanical implant failure

The potential drop-outs by any reason are recognized and reported, despite the lack of 2-year follow-up data, whilst no comparisons at end-point are available.

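### MRI is scheduled only in test-device children but feeds adverse events reported per group, so detection differs between arms; for union, angulation and malunion the protocol contradicts itself on whether MRI counts

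*Protocol*

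**What the plan says.** **Who is scanned, and when.** The Synopsis, under Criteria for Evaluation, lists "Magnetic resonance imaging for a randomly selected subgroup of at least 10 patients treated by test device, general questionnaires". Secondary Objectives gives the purpose, "Soft-tissue reaction against the biodegradable implant are to be studied by Magnetic Resonance Imaging (MRI"), again in at least 10 randomly chosen patients. The footnote to Table 2 (1.1.7) gives another number and names no arm: "Radiographic outcome and bone union formation of 5-10 subjects will be evaluated by MRI imaging immediately after operation and three follow up visits". Table 2 marks MRI after the operation and at weeks 12, 52 and 104. Plain films are marked before and after the operation and at weeks 4, 12, 26 and 104. Week 52 is a call, with no film. No section schedules MRI for control children.

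**What is read from MRI.** The MR Imaging list in 1.1.10 includes union, "fracture malunion (radial bow, Limb-length discrepancy"), soft-tissue reactions, and "complications related to injury or treatment (implant related osteolysis and detection of IM nail failure"). The plain-film list in the same section covers union and osteolysis but not nail failure.

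**How events are reported.** Section 1.1.13 states: "Incidence of adverse events (AE) and serious adverse event (SAE) will be expressed as proportion per group". Its monitored events include union problems, osteolysis, biocompatibility reactions and mechanical failure of the implant. It does not restrict the source of a finding.

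**Which method determines union.** Section 1.1.12 opens with "Forearm's plain radiographs in AP and lateral projections and MRI imaging will be used to determine" and then lists reduction, angulation and union. Secondary Objectives names plain radiography as the method for these same variables. Section 1.1.10 defines union and angulation on the two film views and radial bow on the anteroposterior film.

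**The concern.** A proportion per group is interpretable as a comparison only if both groups are searched in the same way. Here part of one arm has four extra MRI examinations and the other arm has none. One of them falls at week 52, when nobody else is scheduled for imaging. A silent lesion can become an event in a test-device child and stay unknown in a control child. If the complication rate then came out higher with the new nail, the trial could not say whether the device or the closer inspection was the cause.

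A second issue lies in the radiographic outcomes. If 1.1.12 is followed, MRI helps to classify union and angulation in one arm only. If Secondary Objectives is followed, it does not. The protocol leaves both readings open.

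**Working it through.** **1. Arm size.** Statistics gives 13 per arm. With a two-sided alpha of 0.05, a difference of 7.0 degrees, 80% power and the pronation SD of 6.1 degrees, an unpaired t-test needs 13 per arm (power at 13: 80.1%), so the figure reproduces. With the supination SD of 7.6 it would be 20 per arm, and power at 13 would be 61.5%. Here 13 serves only as a denominator.

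**2. MRI coverage, f = m/n.** The number scanned, m, is 10 (Synopsis, Secondary Objectives) or as few as 5 (Table 2 footnote). The arm size, n, is 13, or 17 to 18 if the 35 enrolled children split about evenly (assumption).

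| | n = 13 | n = 17 | n = 18 |
|---|---|---|---|
| m = 5 | 38% | 29% | 28% |
| m = 10 | 77% | 59% | 56% |
| Controls | 0% | 0% | 0% |

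The wording in the Synopsis sets a minimum, so under it 77% of 13 is a floor.

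**3. Weight of one child.** 1/13 = 7.7 percentage points.

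**4. Overlap between monitored events and imaging sources.**

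| Event in 1.1.13 | Plain-film list in 1.1.10 (both arms) | MRI list in 1.1.10 (test subgroup) |
|---|---|---|
| Union problems | yes | yes |
| Osteolysis | yes | yes |
| Implant failure | not listed | listed |
| Biocompatibility reaction | not listed | soft-tissue reactions (nearest match, my inference) |

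Each event has an added or sole imaging route in the test subgroup.

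**5. Possible size.** The protocol gives no detection rates, so both models below rest on assumed inputs.

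*Model A.* Rise in the test-arm proportion = f × q, where q is the share of scanned children with a reportable finding seen only on MRI and no other event. For q from 0.10 to 0.30:
- 10 of 13: 7.7 to 23.1 points
- 5 of 13: 3.8 to 11.5 points
- 10 of 18: 5.6 to 16.7 points
- 5 of 18: 2.8 to 8.3 points

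*Model B.* The true rate p is equal in both arms, film sensitivity is s in both, and film plus MRI detects everything. Test = p[f + (1 − f)s]; control = ps; difference = p·f·(1 − s). Take p from 0.10 to 0.30, s from 0.5 to 0.9, m of 5 or 10, and n of 13 or 17:
- Lowest: 0.10 × 5/17 × 0.1 = 0.3 points (ratio of detected events 1.03).
- Highest: 0.30 × 10/13 × 0.5 = 11.5 points (ratio 1.77).
- Example with p = 0.20, s = 0.7, f = 10/13: test 0.20 × (0.769 + 0.231 × 0.7) = 18.6%; control 0.20 × 0.7 = 14.0%.

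If only common sources count, both arms show ps under Model B and the difference is 0.

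**The case against.** **Union is already defined on films.** A reader might infer from 1.1.12 that two imaging methods classify union in one arm and one method in the other. The documents do not support that as a settled fact. Secondary Objectives names plain radiography, the Synopsis links bone union to plain films, and 1.1.10 gives film-based definitions that apply to every child. This part of the objection stands. What remains is that 1.1.12, and the MRI row and footnote of Table 2, say otherwise.

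**MRI may correct a gap for nail failure.** The device description mentions X-ray markers only in the tips of the test nail, and failure is listed only under MRI. A break along the shaft may therefore be hard to see on film (an inference), and MRI could offset under-detection in the test arm. A strict film-only rule would then hide test-arm failures. This stands and shapes the fix.

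**Controls have their own extra look.** Nail removal under anaesthesia at 6 months is an occasion for observation that test-device children lack. This is true, so removing MRI alone would not make detection fully equal. It does not justify mixing MRI findings in.

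**The safety text does not name MRI, specifies no test, and the SAP may settle event sources.** The safety sources are physical and radiographic examinations, and nowhere is a silent MRI finding called an event. But 1.1.10 places MR imaging under its radiographic heading, and 1.1.13 has no exclusion. An unseen SAP might restrict sources. The protocol as written does not, and its contradiction on union would remain.

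**Conclusion.** The concern holds for adverse events. Followed as written, the plan gives unequal detection in the per-group proportions, through MRI in 38% (5 of 13) or 77% (10 of 13) of a 13-child test arm and in no controls. For findings that MRI adds, such as osteolysis, the test-arm proportion can only go up, which works against the new device. For nail failure MRI may instead offset a blind spot.

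The size cannot be computed from the documents. The illustrations run from 0.3 to 23.1 points depending on the assumed rates. The upper end requires 10 of 13 children scanned, MRI-only findings in 30% of them, each counted as an event, and no other event in those children. The firm figure is that one child in 13 is 7.7 points.

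For union, angulation and malunion the finding is narrower: the sections disagree on method and must be reconciled. Biased classification is a risk from that disagreement, not an established feature of the plan. The same union problems are also monitored adverse events, so they are exposed by that route. Osteolysis is read on films in both arms, so only its MRI-only part is affected. The primary range-of-motion comparison is untouched.

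**What to change.** 1. **Section 1.1.12:** remove MRI from the compared reduction, angulation and union variables, so that the section agrees with Secondary Objectives and 1.1.10. Align the MRI row and footnote of Table 2. Keep MRI as a descriptive assessment in the test arm.
2. **Section 1.1.13:** base the between-group adverse-event proportions on sources common to both arms: visits, calls and plain films. Record on the CRF how each event was first detected; the same field would identify events first seen at titanium-nail removal. Report MRI-only findings in full beside that comparison, with a second version of the proportions that counts them. Always show nail failures detected by MRI.
3. **Synopsis, Secondary Objectives and Table 2 footnote:** state one MRI subgroup size and name the arm in each place.

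The cost is protocol wording, one CRF field and one additional adverse-event display. The common-source comparison leaves out MRI-only findings and must be read with the second display. No safety information is lost.
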